5.3.2 Exclusion Criteria

Patients will not be enrolled in this study if they meet any of the following criteria:

1. Females who are pregnant or lactating.
2. MGFA Class I, IVb, and V.
3. Have an active infection, a recent serious infection (i.e., requiring injectable antimicrobial therapy or hospitalization) within the 8 weeks prior to Screening; or history of or known infection with human immunodeficiency virus (HIV), hepatitis B virus (HBV), hepatitis C virus (HCV), or *Mycobacterium tuberculosis*. Patients must have negative test results for HBV surface antigen, HBV core antibody, HCV antibody, HIV 1 and 2 antibodies, and a negative QuantiFERON[®]-TB Gold test at Screening. Patients with an indeterminate QuantiFERON[®]-TB Gold result will be allowed one retest; if not negative on retesting, the patient will be excluded.
4. At Screening, have clinically significant laboratory abnormalities or as below:
 - Aspartate aminotransferase (AST) and alanine aminotransferase (ALT) $> 2 \times$ upper limit of normal (ULN).
 - Total serum bilirubin of $> 1.5 \times$ ULN (except for Grade 1 hyperbilirubinemia solely due to a medical diagnosis of Gilbert's syndrome).
 - Serum creatinine > 1.5 mg/dL and creatinine clearance < 50 ml/min (using the Chronic Kidney Disease Epidemiology [CKD-EPI]-Creatinine formula).
 - Clinically significant proteinuria (i.e., $> 3 \times$ ULN)
 - Hemoglobin ≤ 9 g/L
 - Thyroid stimulating hormone or thyroglobulin outside of the central laboratory normal range.
 - International normalized ratio (INR) or activated partial thromboplastin time (aPTT) $> 1.2 \times$ ULN.
 - Total immunoglobulin G level < 6 g/L.
5. Body Mass Index (BMI) at Screening ≥ 35 kg/m².
6. Use of rituximab, belimumab, eculizumab or any monoclonal antibody for immunomodulation within 6 months prior to first dosing. Patients with prior exposure to

rituximab must have CD19 counts within the normal range per the central laboratory at Screening.

7. Use of any biological therapy or investigational drug within 3 months or 5 half-lives of the drug (whichever is longer) before Screening.
8. Immunoglobulins given by IV (IVIg), or intramuscular route, or plasmapheresis/plasma exchange (PE) within 4 weeks before Screening.
9. Have known autoimmune disease other than MG that would interfere with the course and conduct of the study (such as uncontrolled thyroid disease or severe RA).
10. Have received vaccinations within 4 weeks before Screening or have any vaccinations planned during the study.
11. Have a history of malignancy, including malignant thymoma, or myeloproliferative or lymphoproliferative disorders at any time, unless deemed cured by adequate treatment with no evidence of recurrence for ≥ 5 years before Screening. Patients with completely excised non-melanoma skin cancers (such as basal cell carcinoma or squamous cell carcinoma) or cervical carcinoma in situ would be permitted at any time.
12. Have a history of cerebrovascular accident or myocardial infarction within the last 12 months before Screening, or current severe/unstable angina, arrhythmia, symptomatic congestive heart failure New York Heart Association (NYHA) class III or IV, or uncontrolled hypertension.
13. Have clinical evidence of significant unstable or uncontrolled acute or chronic diseases (i.e., cardiovascular, pulmonary, hematologic, gastrointestinal, endocrinologic, hepatic, renal, neurologic, malignancy, or infectious diseases) which, in the opinion of the Investigator, could confound the results of the study or put the patient at undue risk.
14. Major past surgery (e.g., heart valve replacement, hip replacement) that, in the opinion of the Investigator, poses a risk to patient's safety or interferes with the study evaluation, procedures or completion.
15. Thymectomy when performed < 3 months prior to Screening.
16. History or presence of alcoholism or drug/chemical/substance abuse within 2 years before Screening per Investigator's opinion.

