6.2 Screening

After informed consent has been obtained, patients will be screened at the site for eligibility based on the inclusion and exclusion criteria defined in [Section 5.3.1](#) and [5.3.2](#) respectively. Screening procedures must be performed within 15 days prior to randomization.

In addition to obtaining written informed consent, the following assessments will be performed at Screening:

- Assign patient Screening number via IxRS.
- Eligibility evaluation (review of inclusion and exclusion criteria).
- Relevant medical and surgical history, relevant prior medications including all previous treatment/therapies for MG including patient's response and all concomitant medications.
- Complete physical examination including height and weight.
- Vital signs.
- Demographic data (date of birth, gender, race, and ethnicity).
- Efficacy assessments in the order of MGQoL15r, MG-ADL, QMG, and MGC before any other assessments (except for obtaining informed consent).
- Clinical laboratory tests (hematology including hemoglobin, platelet count, white blood cell count with differential count; blood chemistry, including creatinine, creatinine clearance, blood urea nitrogen [BUN], glucose, alanine aminotransferase [ALT], aspartate aminotransferase [AST], total bilirubin, gammaglutamyl transferase [GGT], C-reactive protein [CRP], alkaline phosphatase, lactate dehydrogenase, uric acid, albumin, potassium, sodium, calcium, thyroglobulin, International normalized ratio or activated partial thromboplastin time (aPTT), and CD19 counts).
- ECG.
- Urinalysis.
- Serum Pregnancy test.
- Viral and bacterial tests (including surface antigen of hepatitis B virus [HbsAg] and anti-hepatitis C antibodies, HIV, and tuberculosis serology).
- Suicidality assessment.
- Assess AEs if any.

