6.3 Randomization

The results of all Screening procedures must be available prior to randomization at Visit 1 to determine eligibility for randomization into the study. If a patient meets all the study

argenx
ARGX-113-1602, Version 2.0
ARGX-113

eligibility criteria, the Investigator will randomize the patient at Visit 1 via IxRS; if the patient is not eligible, then the patient should be recorded as a screen failure in the IxRS.

On completion of Screening and randomization, study patients will be instructed not to participate in any other clinical study that involves an intervention or collection of data until the completion of the current study.

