10.1 Determination of Sample Size

Approximately 36 patients will be screened in order to randomize approximately 24 patients (12 patients per treatment arm) to get at least 20 patients who have received at least 3 doses of IMP (either ARGX-113 or placebo) and who completed at least 2 weeks of follow-up period post last dose (See [Appendix 14.6](#)). Patients may be replaced in certain circumstances. Possible scenarios in which a patient may be replaced is mentioned in [Table 2](#). Final decision for replacement of patients will be done on a case-by-case basis in consultation with the [Medical Monitor](#) at the Sponsor's designated contract research organization (CRO, Quintiles) and/or the [Medical Director](#) at the Sponsor's end.

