10.4.1.2 Vital Signs Measurements, Physical Findings and Laboratory assessments

Summaries and listings of data for vital signs, hematology, clinical chemistry and urinalysis laboratory tests, ECGs, suicidality assessments, and physical examination findings will be presented. Appropriate data will be summarized for the observed value at each scheduled assessment and for the corresponding change from Baseline.

For hematology and clinical chemistry tests, listings of patient data will also flag up any abnormal or out-of-range values. Clinically significant changes in the laboratory test parameters will be summarized and listed. Hematology and clinical laboratory data will be reported in System International (SI) units.

For ECG variables, the QT correction factor will be based on both the Bazett and Fridericia formulae (QTcB and QTcF). Categorical summaries of absolute QT, QTcB and QTcF values and change from (Baseline) values in QT, QTcB and QTcF values will be presented by treatment and visit.

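### The haemoglobin exclusion limit is printed as 9 g/L (0.9 g/dL) in both the synopsis and Section 5.3.2, so the numeric cut-off screens out no plausible candidate

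*Protocol*

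**What the plan says.** Criterion 4 in Protocol Section 5.3.2 lists laboratory exclusions at Screening. It opens with a general clause, "At Screening, have clinically significant laboratory abnormalities or as below", followed by specific limits. The haemoglobin limit is "Hemoglobin ≤ 9 g/L". The synopsis prints the same number and unit under the same criterion.

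Neither the protocol nor the SAP gives any other haemoglobin limit. Protocol Appendix 5 (Section 14.5) lists haemoglobin among the haematology tests without a unit or threshold.

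The test feeds directly into eligibility. Section 6.2 includes it among the Screening procedures: "Clinical laboratory tests (hematology including hemoglobin, platelet count, white blood cell count with differential count". Section 6.3 adds: "The results of all Screening procedures must be available prior to randomization at Visit 1".

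**The concern.** A haemoglobin of 9 g/L is 0.9 g/dL, which is far below anything expected in a person attending a screening visit. The number and the unit do not appear to belong together. If the bullet is applied as printed, it never triggers.

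What is at stake is the working of an eligibility rule. Section 5.3.4 requires the entry criteria to be applied strictly. A site that does so has no usable haemoglobin cut-off. A site that silently reads the number in another unit is applying a criterion the protocol does not contain. With up to 25 sites, practice could differ. The primary objective is safety, and laboratory assessments are part of the primary endpoint, so numeric laboratory entry limits ought to be usable as written.

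**Working it through.** The limit is a stated threshold, not a computed result, so there is no calculation of the plan's to reproduce. The check is a unit conversion, a comparison with assumed candidate values, and a reading of the surrounding text.

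**Inputs**
- Haemoglobin limit: 9 g/L or below (synopsis and Section 5.3.2, criterion 4).
- Planned Screening number: "Approximately 36 patients will be screened in order to randomize approximately 24 patients" (Section 10.1).
- Haemoglobin of screening candidates: not in the documents. Three assumed ranges are used: 20 to 110 g/L, 50 to 170 g/L and 70 to 160 g/L.

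**Conversion**

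g/dL = (g/L) ÷ 10, so 9 ÷ 10 = 0.9 g/dL.

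**Comparison with the assumed ranges**

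The bullet excludes a candidate only if haemoglobin is at or below 9 g/L. It is enough to look at the lower end of each range.

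| Assumed range (g/L) | Lower end ÷ limit | Share excluded by the bullet |
|---|---|---|
| 20 to 110 | 20 ÷ 9 = 2.2 | 0% |
| 50 to 170 | 50 ÷ 9 = 5.6 | 0% |
| 70 to 160 | 70 ÷ 9 = 7.8 | 0% |

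Expected number excluded by the bullet: 0% × 36 = 0.

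**Could it be a fault in the text extraction?**

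This is unlikely. The same unit appears in two separately laid-out places, a synopsis table and a list in the body. A per-decilitre unit survives intact in the same list: "Serum creatinine > 1.5 mg/dL and creatinine clearance". The IgG limit in that list is in g/L and is also intact. Nothing is redacted at this point.

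**Does other text resolve it?**

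Section 10.4.1.2 says: "Hematology and clinical laboratory data will be reported in System International (SI) units". It concerns reporting and sets no limit. It gives no reason to read the bullet in a unit other than the printed one; haemoglobin can be reported in g/L, so it makes the literal reading more natural.

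**What still excludes an anaemic patient?**

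Two clauses do, both resting on judgement. One is the opening of criterion 4. The other is criterion 13, which begins "Have clinical evidence of significant unstable or uncontrolled acute or chronic diseases (i.e., cardiovascular, pulmonary, hematologic" and depends on the investigator's opinion. Neither supplies a number. How many patients they would exclude cannot be estimated from the documents.

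**The case against.** The strongest reply is that this is a self-evident unit slip with little consequence. The numeric bullets are alternatives to the general clause on clinically significant abnormalities, so a clinically important low haemoglobin is excluded whatever the bullet says. Criterion 13 covers serious haematologic disease as well, and Section 8.1.2 has laboratory results reviewed for clinical significance throughout the study. A clinician would probably query the value and not apply it literally. The synopsis and Section 5.3.2 agree with each other, so the documents do not contradict themselves. The mismatch is visible only with outside knowledge of haemoglobin values. Finally, the 0 of 36 follows by construction, because every assumed range starts above 9 g/L.

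Much of this stands. Anaemic patients are not made automatically eligible. What is lost is a uniform, objective cut-off, not all protection. The two places do agree: this is one implausible pairing of number and unit printed twice. The 0% figure says only that the bullet does no work. It does not estimate how many patients a working limit would have excluded, which is unknown and could also be zero.

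The reply does not rescue the bullet. The judgement clauses supply no threshold, and the protocol lists a numeric limit in addition to them. Eligibility should not depend on each site guessing the intended unit, especially where the protocol asks for the criteria to be followed strictly. The plausibility assumption is outside the documents, but it is mild: even 20 g/L is more than twice the printed limit.

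**Conclusion.** The concern holds. As printed, the haemoglobin limit equals 0.9 g/dL and excludes 0 of the roughly 36 patients planned for Screening under every range examined. The one assumption is that no candidate able to attend Screening has a haemoglobin as low as 9 g/L.

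The consequence is limited to eligibility. For haemoglobin, the objective part of criterion 4 is inoperative and the decision passes to judgement. Endpoints, sample size and planned analyses are untouched, and nothing here suggests bias between arms. It should be fixed because it is a wrong threshold in an entry criterion of a trial whose primary objective is safety, and because the correction is simple. No view is taken on whether the other limits in criterion 4 are workable.

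**What to change.** The sponsor should confirm the intended value and unit, then make the identical correction in the synopsis and in Section 5.3.2, criterion 4. Sites should be told of the correction. The documents do not show whether recruitment was still open; if it had closed, the study report should state the discrepancy and how sites applied the criterion. The choice of limit belongs to the sponsor, and none is proposed here.

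The cost is a two-line protocol correction and a site notice. The SAP needs no change.

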5.3.3 Patient Withdrawal from Study

Patient withdrawal in this study only refers to patients withdrawn due to withdrawal of consent. Any other circumstances for early dropout of a patient from the study treatment or study will be referred to as early discontinuation (see Section 5.3.4).

All patients are free to withdraw consent from participation in the study at any time, for any reason, specified or unspecified, and without prejudice to further treatment.

Prior to actual withdrawal of consent, an effort should be made to perform a final set of assessments as per Visit 16/EoS/ED visit in the Schedule of assessments ([Table 1](#)).

5.3.4 Early Discontinuation from the Study Treatment or Study

The criteria for enrollment and randomization are to be followed explicitly. If it is noted that a patient who does not meet the inclusion and exclusion criteria is inadvertently randomized and dosed, the [Medical Monitor](#) at Sponsor's designated CRO (Quintiles) and the Sponsor's [Medical Director](#) must be contacted immediately for discussion on how to proceed with the patient. The patient should be discontinued from the study if there is any compelling safety concern for the patient to continue. The various scenarios that may occur leading to discontinuation of the patient from study and/or treatment is detailed in [Table 2](#).

Table 2 Potential Scenarios for Early Discontinuation from Study and Treatment

Scenario	Discontinuation from Study Treatment	Discontinuation from Study	Replacement if necessary
Safety Concern during Treatment period: In case of a safety concern during Treatment period , Medical Monitor should be consulted and the safety and efficacy assessments per Follow-up period of Table 1 (Visit 9 to Visit 16) must be completed wherever possible.	Discontinue patient from Study Treatment.	Patient does not need to be discontinued from the study depending on the severity and nature of safety event but discontinuation from the study needs to be discussed with the Medical Monitor and/or Sponsor's Medical Director . Wherever possible and appropriate/safe, the patient should continue the schedule of assessments for the Follow-up Period of Table 1 (Visit 9 to Visit 16).	Patients will be analyzed as part of Safety and Efficacy analysis and such a patient will not be replaced.
Safety Concern after Treatment period: In case of a safety concern after Treatment period , the safety and efficacy assessments per Follow-up period of Table 1 (Visit 9 to Visit 16) must be completed where possible and Medical Monitor should be consulted.	Not Applicable.	Patient does not need to be discontinued from the study depending on the severity and nature of safety event but discontinuation from the study needs to be discussed with the Medical Monitor and/or Sponsor's Medical Director . Wherever possible and appropriate/safe, the patient should continue the schedule of assessments in the Follow-up Period of Table 1 (Visit 9 to Visit 16).	Patients will be analyzed as part of Safety and Efficacy analysis and such a patient will not be replaced.
Disease deterioration during Treatment period	After consultation with the Medical Monitor , discontinue patient from Study Treatment, initiate rescue therapy and follow-up for 30 days after the early discontinuation visit or until satisfactory resolution/stabilization.	After consultation with Medical Monitor and prior to start on rescue therapy, all Visit 16 assessments should be completed. Patients will be discontinued from the study and followed up for safety for an additional 30 days or until satisfactory resolution/stabilization.	Patients will be analyzed as part of Safety and Efficacy analysis and such a patient will not be replaced
Disease deterioration after Treatment period: In case of disease deterioration after Treatment period , the safety and efficacy assessments per Follow-up period of Table 1 (Visit 16) must be completed along with a follow-up for 30 days after the early discontinuation visit or until satisfactory resolution/stabilization where possible and Medical Monitor should be consulted.	Not Applicable.	Patient's study continuation must be assessed by the Investigator, discussed with the Medical Monitor and/or Sponsor's Medical Director based on clinical examination. Possible examples of worsening include: 
 • Severe deterioration where it may not be possible for patient to continue in the study. • The "End of Treatment Effect" whereby the patient's condition is worsening after any initial improvement while on the study. Prior to initiating rescue therapy, all Visit 16 assessments should be completed and patient should be followed up for safety for an additional 30 days or until satisfactory resolution/ stabilization.	Patients will be analyzed as part of Safety and Efficacy analysis and such a patient will not be replaced

Scenario	Discontinuation from Study Treatment	Discontinuation from Study	Replacement if necessary
Voluntary Discontinuation from IMP or Major Protocol Deviation(s) possibly leading to (Details in a separate Manual) discontinuation from IMP during Treatment period: The Schedule of Assessments for dosing and safety and efficacy evaluations per Table 1 must be performed whenever possible and must be discussed with the Medical Monitor on a case-by-case basis.	In case of voluntary discontinuation during Treatment period or any major protocol deviation(s) possibly leading to discontinuation from IMP during treatment period, a patient should be discontinued from the study treatment.	Patient does not need to be discontinued from the study but discontinuation from the study needs to be discussed with the Medical Monitor and/or Sponsor's Medical Director . And wherever appropriate, patient should continue the schedule of assessments.	Patient will not be replaced if he/she receives at least 3 infusions and completes the Follow-up assessments as indicated in Table 1 with at least 2 weeks of Follow-up post last dose. Patient may be replaced if he/she receives less than 3 infusions and/or cannot complete at least 2 weeks of Follow-up post last dose as indicated in Table 1 .
Major Protocol Deviation(s) (Details in a separate Manual) after Treatment period: The safety and efficacy assessments per Follow-up period of Table 1 (Visit 8 to Visit 16) must be completed where possible and Medical Monitor should be consulted.	Not Applicable.	Patient does not need to be discontinued from the study but discontinuation from the study needs to be discussed with the Medical Monitor and/or Sponsor's Medical Director . Wherever appropriate, patient should continue the schedule of assessments.	Such patients may only be replaced they cannot complete at least 2 weeks of Follow-up post last dose as indicated in Table 1 .

During the study, in case of situations that occur apart from the scenarios described above, the decision to replace patients must be made on a case-by-case basis in consultation with the [Medical Monitor](#) at the Sponsor's designated contract research organization (CRO, Quintiles) and/or the [Medical Director](#) at the Sponsor's end.

In addition, patients must be discontinued early from the study in the following circumstances:

- Pregnancy.
- Lack of efficacy as judged by the Investigator.
- Emergency unblinding.
- Physician decision.
- Lost to follow up.
- On request of the Sponsor.

For patients who discontinue the study early, all the procedures as those listed for the Early Discontinuation (ED) visit (same procedures as for the End-of-Study [EoS] visit or Visit 16) in the Schedule of Assessments ([Table 1](#)) are to be performed (early discontinuation visit).

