*: The allowed window period between visits in Treatment period and Follow-up period is ± 1 day provided that 2 consecutive visits are 3 days apart at a minimum. Every effort should be made to schedule every visit on the exact Day (which is relative to the Baseline visit or [Visit 1]) as described in above Schedule of Assessments ([Table 1](#)) without the window.

**: The Visits 2, 4, 6, and 8 are optional.

- a. To take place within 15 days prior to first administration of the Investigational Medicinal Product (IMP) at Visit 1.
- b. No study-related assessment is to be carried out before the patient has signed informed consent.
- c. A complete physical examination will be performed at Screening, Visit 7, and at Visit 16/EoS/ED. An abbreviated examination will be done at all other visits. On dosing days, physical examination including weight measurement should be performed pre-dose.
- d. Height should only be measured at Screening (and Body Mass Index [BMI] to be calculated accordingly at Screening only).
- e. Randomization to be performed only after confirmation of eligibility of the patient including the MG-ADL score assessed at Visit 1 and prior to dosing at Visit 1. The assessments for vital signs, urinalysis, and anti-drug antibodies, must be performed pre-dose at visits when the Investigational Medicinal Product (IMP) is administered (Visits 1, 3, 5, and 7). **Efficacy assessments** scheduled on designated Days should be completed pre-dose on each dosing day and **should be performed prior to any other study specific assessment**, except for obtaining informed consent at Screening. **Efficacy assessments** should be performed in the following sequence (at each study visit including these assessments): **MGQoL15r, MG ADL, QMG, and MGC**. Cholinesterase inhibitors must be held for at least 12 hours before the MGQoL15r, MG-ADL, QMG, and MGC assessments (consistent with the revised manual for the QMG test as recommended by the Myasthenia Gravis Foundation of America Inc [MGFA])¹. A total score ≥ 5 on the MG-ADL with more than 50% of this score attributed to non-ocular items should be met at both Screening and Baseline (Visit 1) to confirm eligibility.

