3.1. GENERAL DESCRIPTION

This is a randomized, double-blind, placebo-controlled, multicenter Phase II study to evaluate the safety, tolerability, efficacy, pharmacokinetics, pharmacodynamics and immunogenicity of ARGX-113 for the treatment of autoimmune Myasthenia Gravis (MG) with generalized muscle weakness.

Approximately 24 subjects will be randomized in a 1:1 ratio to receive either ARGX-113 (10 mg/kg) or matching placebo via intravenous (IV) infusion in addition to Standard of Care (SoC) over a period of 2 hours during the treatment period, i.e. on Days 1 (Visit 1), 8±1 (Visit 3), 15±1 (Visit 5), and 22±1 (Visit 7). The Treatment period consists of 7 visits (of which the 3 visits between the weekly dosing visits are optional).

A schematic of the study design is included as Figure 1.

Figure 1: Schematic of Study Design

Document: CCI
 Author: PPD
 Version Number: 1.0
 Version Date: 06 Oct 2017
 Template No: CCI
 Effective Date: 01Apr2016
 Reference: CCI

The study will include a screening period of at most 15 days, a treatment period of 3 weeks (4 infusions administered one week apart) from Visit 1 to Visit 7 and a follow-up (FU) period of 8 weeks starting after completion of Visit 7 to Visit 16.

Although the FU period is from Visit 8 to Visit 16, the FU in fact starts immediately after the last Investigational Medicinal Product (IMP) infusion at Visit 7.

The total dose per IMP infusion is capped at 1200 mg for subjects with body weight \geq 120 kg

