6.5. WINDOWING CONVENTIONS

No visit windowing will be performed for this study.

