8. OUTPUT PRESENTATIONS

The Mock Shells provided with this SAP describe the format, layout and content of the summary tables, figures and listings to be provided by QuintilesIMS Biostatistics. This document will be a working document and updates will be documented in its modification history.

All visit assessments will be presented according to the nominal visit name. Study populations will be summarized and listed as well.

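### Table 2 limits a patient stopped for a safety concern during treatment to Visits 9 to 16, so the remaining scheduled Visit 3, 5 and 7 assessments drop out by rule and the timing of Visit 9 is left open.

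*Protocol*

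**What the plan says.** Protocol Section 5.3.4, Table 2, has a row for a safety concern arising during the Treatment period. The patient stops study drug and stays in the study where possible. The scenario cell says that "the safety and efficacy assessments per Follow-up period of Table 1 (Visit 9 to Visit 16) must be completed wherever possible". The study-discontinuation cell repeats the range: where possible and safe, "the patient should continue the schedule of assessments for the Follow-up Period of Table 1 (Visit 9 to Visit 16"). Such patients stay in the safety and efficacy analyses and are not replaced.

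The row for voluntary discontinuation, or a major deviation that may lead to stopping study drug, in the same period reads differently: "The Schedule of Assessments for dosing and safety and efficacy evaluations per Table 1 must be performed whenever possible". It sets no Visit 9 to 16 limit.

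The footnote to Table 1 fixes the calendar: "Every effort should be made to schedule every visit on the exact Day (which is relative to the Baseline visit or [Visit 1"]). Section 6.0 says the same. Section 5.1 adds that follow-up begins right after the last infusion, but describes this only for an infusion at Visit 7.

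In the SAP, Section 6.5 states "No visit windowing will be performed for this study" and Section 8 states "All visit assessments will be presented according to the nominal visit name". Section 6.4 leaves unscheduled measurements out of by-visit summaries and efficacy analyses, but keeps them in listings.

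**The concern.** The Visit 9 to 16 range also appears in the row for a safety concern after the Treatment period. It fits there, because dosing is over. It does not fit a patient whose last infusion was at Visit 1, 3 or 5, for whom up to three scheduled assessment visits still lie ahead. Followed literally, the row removes those visits by rule for patients who have just had a safety event.

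Safety is the primary objective, and vital signs, ECG and laboratory assessments are part of the primary endpoint. The by-visit tables for Visits 3, 5 and 7 would then lack patients selected by a safety event. For efficacy, SAP Section 7.3 leaves the missing scores to the mixed model, although their absence is linked to safety in a trial with about 12 patients per arm.

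The row also does not say when Visit 9 takes place if the last infusion came early. A site could keep Day 29, or could hold Visit 9 one week after the last infusion. The second choice would put data from one week after one to three infusions under the same visit label as data from one week after four.

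**Working it through.** **Inputs.** Visits 1, 3, 5, 7, 9 and 16 are on Days 1, 8, 15, 22, 29 and 78 (Protocol Table 1). Post-baseline efficacy visits are 3, 5, 7, 9, 10, 11, 12, 14 and 16, nine in all (Section 4.2). Anti-drug antibodies are sampled before dosing at Visits 1, 5 and 7, and ECGs are done at Visits 1 and 7 (Section 6.4.1). SAP Section 7.2 plans 12 patients per group.

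**Planned schedule.** Visit 7 to Visit 16 is 78 − 22 = 56 days, which matches the stated 8-week follow-up. Visit 7 to Visit 9 is 29 − 22 = 7 days, the planned interval from last infusion to Visit 9.

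**Literal reading: Visit 9 stays on Day 29.** Gap = 29 − day of last infusion. The range lets Visit 9, and any last infusion after Day 1, move by one day each.

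| Last infusion | Gap to Visit 9 (days) | Range (days) | Efficacy visits dropped | Also dropped |
|---|---|---|---|---|
| Visit 1, Day 1 | 29 − 1 = 28 | 27 to 29 | 3, 5, 7 (3 of 9) | antibody samples at Visits 5 and 7, ECG at Visit 7 |
| Visit 3, Day 8 | 29 − 8 = 21 | 19 to 23 | 5, 7 (2 of 9) | antibody samples at Visits 5 and 7, ECG at Visit 7 |
| Visit 5, Day 15 | 29 − 15 = 14 | 12 to 16 | 7 (1 of 9) | antibody sample and ECG at Visit 7 |

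The laboratory tests, urinalysis, vital signs and non-optional pharmacodynamic samples of the dropped visits go with them. Beyond the planned 7 days, the excess is 21, 14 or 7 days.

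**Shifted reading: Visit 9 is held 7 days after the last infusion.** Visit 9 then falls on Day 1 + 7 = 8, 8 + 7 = 15 or 15 + 7 = 22, the nominal days of Visits 3, 5 and 7. Filed as Visit 9, the data are 29 − 8 = 21, 29 − 15 = 14 or 29 − 22 = 7 days early. Visit 16 moves to Day 78 − 21 = 57, 78 − 14 = 64 or 78 − 7 = 71.

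**Weight of one patient.** 1/12 = 8.3% of an arm. The documents do not say how far a score on the true day would differ from the Day 29 score. If the difference is assumed to be 1 to 4 points, one misfiled patient moves the raw Visit 9 arm mean by 1/12 = 0.08 to 4/12 = 0.33 points.

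**With the Table 1 assessments kept on their days.** No efficacy visit is dropped by rule, the longest gap between efficacy visits up to Day 50 is 7 days, and no value carries a wrong nominal visit. The sample size does not change.

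**The case against.** The strongest reply is that patient observation does not depend on this row.

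- The synopsis and Section 5.1 promise safety follow-up, and efficacy follow-up where possible, to anyone stopping for safety.
- Adverse events and concomitant medication are monitored continuously (Table 1 footnotes). Section 8.1.1.3 requires active follow-up of events after the last dose.
- Section 6.7 allows unscheduled visits for this purpose, and Section 8.1.2 allows extra safety samples.
- Adverse event incidence is tabulated by system organ class and preferred term, so the by-visit exclusion of unscheduled data does not touch it.

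All of this stands. A reader might infer that a patient who stops for safety goes unobserved for up to four weeks, or is watched less closely than one who stops by choice. The documents do not support that. The difference is in what is scheduled, and the voluntary row is itself qualified by feasibility and case-by-case discussion.

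Two further replies stand in part. First, the shifted reading departs from the stated anchor to Visit 1, so misfiled data are a risk and not what the plan prescribes. The risk remains because the start of follow-up is not defined for an earlier last infusion, and listings would show the true study day without correcting the analysis. Second, the gaps run from the last infusion. If the concern is found at a dosing visit after that visit's pre-dose assessments, those data already exist and the gap in data is shorter. The 14-day case also equals the planned efficacy interval between Visits 12 and 14 (Days 50 and 64), although laboratory tests stay weekly there.

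What is not answered is the by-visit data. Unscheduled results are discretionary, and SAP Section 6.4 keeps them out of by-visit summaries and efficacy analyses.

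**Conclusion.** The point holds for scheduled by-visit safety, pharmacodynamic and efficacy data. Followed literally, the safety-concern row leaves 28, 21 or 14 days from last infusion to the next listed assessment, and drops 3, 2 or 1 of 9 post-baseline efficacy visits with the associated laboratory, vital-sign, antibody and ECG data. This rests on Table 1 days being counted from Visit 1, which the protocol states, and on sites following the row as written.

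The misfiling of Day 8, 15 or 22 data as Visit 9 is secondary and conditional on a site counting from the last infusion. The documents do not support a claim that adverse event capture fails or that the adverse event analysis is affected.

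The overall effect depends on how many patients stop for safety, which the documents do not project. In an exploratory trial of this size, the two rows should be reconciled, but the point does not threaten the study's conclusions by itself.

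**What to change.** 1. Reconcile both cells of the safety-concern row with the voluntary-discontinuation row, for data collection only, so that assessments already scheduled in Table 1 are not dropped by rule where they are possible and safe. Changing one cell alone would create a new contradiction.
2. State the day anchor of Visit 9 when the last infusion was before Visit 7.
3. Make sure, at data entry or in the SAP, that these patients' data are analysed under the visit that matches their actual study day.

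Whether and when study drug stops, and clinical management afterwards, are untouched and stay with the sponsor and the investigator.

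The cost is an edit to two table cells, a sentence on the anchor and a sentence on visit assignment. No visit is added beyond Table 1. The patients affected would carry some extra burden, namely fasting laboratory tests and the 12-hour hold of cholinesterase inhibitors before efficacy scoring. The row's existing allowance for what is appropriate and safe leaves room for that judgement.
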